4.0 Study Objective

4.1 Primary Objectives

The primary objectives of this study are to assess the efficacy by evaluating the percentage of subjects achieving SVR₁₂ (HCV RNA < LLOQ 12 weeks following therapy) and safety of GLE/PIB combination in treatment-naïve adults in Brazil with chronic hepatitis C virus (HCV) genotype (GT) 1 – 6 infection without cirrhosis or with compensated cirrhosis. The efficacy endpoints will be analyzed based on combined

treatment duration and genotypes and safety analysis will be done by individual treatment groups.

4.2 Secondary Objectives

The secondary objectives are to assess efficacy of GLE/PIB based on overall population (i.e., across treatment durations and genotypes) by evaluating the following:

- The percentages of subjects with HCV on-treatment virologic failure (OTVF);
- The percentages of subjects with HCV virologic relapse.

5.0 Investigational Plan

5.1 Overall Study Design and Plan: Description

This is a Phase 3b, open-label, multicenter study to evaluate the efficacy and safety of GLE/PIB for an 8- or 12-week treatment duration in adults in Brazil with chronic HCV GT1 – 6 infection, without cirrhosis or with compensated cirrhosis with a METAVIR System Fibrosis Score of F2, F3 or F4 (F2-F4) or equivalent,¹⁶ who are HCV treatment-naïve. Approximately 100 subjects meeting the eligibility criteria will be enrolled. The study enrollment will be monitored to meet the following enrollment criteria: 1) a minimum of approximately 35 GT1 and 35 GT3 subjects and 2) approximately 80 F2 – 3 and a maximum of approximately 20 F4 subjects.

This study will consist of a Screening Period, a Treatment Period and a Post-Treatment Period.

Screening Period: Subjects will have up to 35 days following the Screening Visit to confirm eligibility and enroll in the study.

Treatment Period: Eligible subjects will be enrolled to receive GLE/PIB 300 mg/120 mg once daily (QD) for an 8 (Arm A) or 12 (Arm B) week treatment duration based on cirrhosis status.

Post-Treatment Period: Subjects who complete or prematurely discontinue the Treatment Period will be followed for 12 weeks to monitor HCV RNA levels to evaluate efficacy and the emergence and persistence of resistance-associated substitutions.

A study schematic is shown below in [Figure 1](#).

Figure 1. Study Design

* The study enrollment will be monitored to meet the following enrollment criteria: 1) a minimum of approximately 35 GT1 and 35 GT3 subjects and 2) approximately 80 F2 – F3 and a maximum of approximately 20 F4 subjects.

Approximately 100 eligible subjects will be enrolled into one of the following treatment arms:

- Arm A: HCV GT 1 – 6 without cirrhosis (F2 – F3) subjects will be treated with GLE/PIB 300 mg/120 mg once daily (QD) for 8 weeks.
- Arm B: HCV GT 1 – 6 subjects with compensated cirrhosis (F4) will be treated with GLE/PIB 300 mg/120 mg once daily (QD) for 12 weeks.

The study was designed to enroll approximately 100 subjects to meet scientific and regulatory objectives without enrolling an undue number of subjects in alignment with ethical considerations. Therefore, if the target number of subjects has been enrolled, there is a possibility that additional subjects in screening may not be enrolled.

5.1.1 Screening Period

At the Screening Visit, subjects who provide written (signed and dated) informed consent prior to any study-specific procedures will receive a unique subject number via the Interactive Response Technology (IRT) system. The investigator will evaluate whether the subject meets all of the eligibility criteria specified in Section 5.2.1 and Section 5.2.2 during the period from the Screening Visit through Study Day 1 prior to dosing, and will record the results of this assessment and the details of the informed consent process in the subject's medical records. Eligible subjects have up to 35 days following the Screening Visit to enroll into the study.

5.1.1.1 Rescreening

Subjects who at Screening have any of the following are not eligible to rescreen or retest:

- A positive Hepatitis B surface antigen (HBsAg);
- HBV DNA > LLOQ in subjects with isolated positive anti-HBc (i.e., negative HBsAg and Anti-HBs); or
- If Woman of Childbearing Potential (WOCBP), a positive serum pregnancy test;
- Development of decompensated liver disease during the screening period, as defined by the Exclusion Criterion 6.

Otherwise subjects may be retested or rescreened only once unless approved by the Primary Therapeutic Area Medical Director.

Subjects who have exclusionary laboratory parameter(s) are allowed to retest on the related panel(s) (e.g., exclusionary ALT requires a repeat chemistry panel) within the same screening period and must meet all eligibility laboratory criteria on any panel that is repeated. If any of the retest result(s) are exclusionary, the subject may not be rescreened again.

Subjects that exceed the initial 35 day screening period should be rescreened for all laboratory and eligibility criteria, not just those that were exclusionary during the first screening attempt (with the exception of HIV, HBV, HCV genotype and subtype, follicle stimulating hormone (FSH), which do not need to be repeated). The FibroScan and liver biopsy do not need to be repeated for rescreened subjects provided that the date of the liver biopsy is within 24 months of the rescreening date and the FibroScan is within 6 months of the rescreening date (Section [5.1.1](#)).

Subjects who rescreen or subjects not meeting the study eligibility criteria must be identified by site personnel as a screen failure in both IRT and EDC systems.

5.1.2 Treatment Period

After meeting the eligibility criteria, subjects will be enrolled via IRT on Study Day 1. Subjects will be administered study drug at the site on Study Day 1, and provided dosing instructions.

Study visits and procedures during the Treatment Period are detailed in [Appendix C](#). Safety and tolerability will be assessed throughout the study. Laboratory testing will include chemistry and hematology as specified in [Table 5](#). Plasma samples for pharmacokinetic analysis and HCV RNA analysis will be collected as detailed in Section [5.3](#) and Section [5.3.1.1](#).

All subjects will continue to return to the site on an outpatient basis as outlined in [Appendix C](#). Sites should ensure that subjects adhere to all study visits. Subjects who cannot complete their study visit per the visit schedule should ensure they do not run out of study drug prior to their next study visit. Compliance is critical to ensure adequate drug exposure.

HCV virologic failure criteria will be evaluated and applied by the investigator as detailed in Section [5.4.1.1](#).

Subjects who prematurely discontinue from the Treatment Period should return for a Treatment Discontinuation Visit and undergo the study procedures as outlined in [Appendix C](#) and as described in Section [5.4.1](#). Subjects who prematurely discontinue from study treatment will continue to be followed in the Post-Treatment Period (see Section [5.1.3](#)).

5.1.3 Post-Treatment Period

All subjects who received at least one dose of study drug will be monitored in the Post-Treatment Period for 12 weeks following the last dose of study drug for safety, HCV RNA, and the emergence and persistence of HCV resistance-associated substitutions.

The Post-Treatment Period will begin the day following the last dose of study drug. Study visits during the Post-Treatment period are detailed in [Appendix D](#) and Section [5.3.1.1](#).

Subjects who prematurely discontinue during the Post-Treatment Period should return to the site for a Post-Treatment discontinuation visit as outlined in [Appendix D](#).

5.2 Selection of Study Population

The study population consists of male and female adults aged 18 years or older with chronic HCV GT1 – 6 infection with METAVIR equivalent fibrosis stage of F2 – F4 (without cirrhosis or with compensated cirrhosis) who are HCV treatment naïve (i.e., subject has never received a single dose of any approved or investigational anti-HCV medication). Subjects with HIV/HCV co-infection and subjects at all CKD stages (CKD Stages 1 – 5) are allowed to participate. Subjects who meet all inclusion criteria and none of the exclusion criteria will be eligible for enrollment into the study.

5.2.1 Inclusion Criteria

1. Male or female, at least 18 years of age at time of Screening.
2. If female, subject must be either

Postmenopausal defined as:

- Age > 55 years with no menses for 12 or more months without an alternative medical cause; or
- Age ≤ 55 years with no menses for 12 or more months without an alternative medical cause AND an FSH level > 40 IU/L; or
- Permanently surgical sterile (bilateral oophorectomy, bilateral salpingectomy or hysterectomy).

OR

- A WOCBP practicing at least one protocol specified method of birth control (Section 5.2.4), starting at Study Day 1 through at least 30 days after the last dose of study drug.

3. Females of childbearing potential must have a negative serum pregnancy test result at Screening, and a negative urine pregnancy test at Study Day 1.

Females of non-childbearing potential (either postmenopausal or permanently surgically sterile as defined in Section 5.2.4) at Screening do not require pregnancy testing.

4. Screening laboratory result indicating HCV GT1-, 2-, 3-, 4-, 5- and/or 6-infection. Mixed and indeterminate genotypes are acceptable.

5. Subject has positive plasma HCV antibody and HCV RNA viral load ≥ 1000 IU/mL at Screening Visit.

6. Subjects who are known to be HCV/HIV co-infected may enroll if they have a positive test result for anti-Human Immunodeficiency Virus antibody at Screening and are:

Naïve to treatment with any antiretroviral therapy (ART) (and have no plans to initiate ART treatment while participating in this study), or on a stable, qualifying HIVART regimen for at least 8 weeks prior to Baseline. (Substituting TDF for TAF as part of the combination regimen is allowed at any time.)

The HIVART regimen must include at least one of the following ARV agents:

- Raltegravir (RAL)
- Dolutegravir (DTG)
- Rilpivirine (RPV)
- Elvitegravir/cobicistat (EVG/COBI)

In addition to the above medications, HIV Ab positive subjects (both without cirrhosis or with compensated cirrhosis) may take a nucleoside/nucleotide reverse transcriptase inhibitor (N(t)RTI) backbone containing any of the following:

- Tenofovir disoproxil fumarate (TDF)
- Tenofovir alafenamide (TAF)
- Abacavir (ABC)
- Emtricitabine (FTC)
- Lamivudine (3TC)

Subjects receiving any other HIV ART in addition to those noted above are not eligible for enrollment in the study.

Subjects on stable HIV ART must have Plasma HIVRNA below 50 copies/mL at Screening (by the COBAS® Ampliprep/COBAS® Taqman HIV-1 Test, v 2.0) and at least once during the 12 months prior to Screening (by an approved plasma HIVRNA quantitative assay including but not limited to: COBAS® Ampliprep/COBAS® Taqman HIV-1 Test, v 2.0 or Abbott RealTime HIV-1 assay).

7. Subject must be documented as without cirrhosis with METAVIR equivalent fibrosis stage of F2 – 3 or with compensated cirrhosis (F4) based on results of a liver biopsy, or FibroScan, or FibroTest score (as described in Section 5.3.1.1).

8. Subjects with compensated cirrhosis only: Absence of hepatocellular carcinoma (HCC) as indicated by a negative ultrasound, computed tomography (CT) scan or magnetic resonance imaging (MRI) within 3 months prior to Screening or a negative ultrasound at Screening. Subjects who have an ultrasound with results suspicious of HCC followed by a subsequent negative CT or MRI of the liver will be eligible for the study.
9. Subject must voluntarily sign and date an informed consent form, approved by an Institutional Review Board (IRB)/Independent Ethics Committee (IEC) prior to the initiation of any Screening or study specific procedures.
10. Subjects must be able to understand and adhere to the study visit schedule and all other protocol requirements.
11. Subjects requiring dialysis should have been receiving dialysis for at least 1 month prior to enrollment, and may be on hemodialysis or peritoneal dialysis.

Rationale for Inclusion Criteria

1, 4 – 11	In order to select the appropriate subject population with appropriate disease characteristics for evaluation
2, 3	The impact of GLE and PIB on human pregnancies has not been established. However, assessment of the completed nonclinical reproductive toxicology studies indicates that there is no drug-related effect on teratogenicity/fetotoxicity. In addition, the compounds are non-genotoxic
10	In accordance with harmonized Good Clinical Practice (GCP)

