5.2 Selection of Study Population

The study population consists of male and female adults aged 18 years or older with chronic HCV GT1 – 6 infection with METAVIR equivalent fibrosis stage of F2 – F4 (without cirrhosis or with compensated cirrhosis) who are HCV treatment naïve (i.e., subject has never received a single dose of any approved or investigational anti-HCV medication). Subjects with HIV/HCV co-infection and subjects at all CKD stages (CKD Stages 1 – 5) are allowed to participate.¹⁷ Subjects who meet all inclusion criteria and none of the exclusion criteria will be eligible for enrollment into the study.

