5.3.1.1 Study Procedures

Informed Consent

Signed study-specific informed consent will be obtained from the subject before any study procedures are performed. Details about how informed consent will be obtained and documented are provided in Section [9.3](#).

Medical History

A complete medical history, including history of tobacco, alcohol and drug use, will be taken from each subject at Screening Visit. The subject's medical history will be updated at the Study Day 1 Visit. This updated medical history will serve as the baseline for clinical assessment.

Physical Examination

A complete physical examination will be performed at visits specified in [Appendix C](#), or upon subject discontinuation. A symptom-directed physical examination may be performed at any other visit, when necessary.

The physical examination performed on Study Day 1 will serve as the baseline physical examination for clinical assessment. Any significant physical examination findings after the first dose will be recorded as adverse events.

Height will be measured only at Screening.

Vital Signs and Weight

Body temperature, blood pressure, pulse, and body weight will be measured at each study visit as specified in [Appendix C](#) and [Appendix D](#). Blood pressure and pulse rate should be measured after the subject has been sitting for at least 3 minutes. The subject should wear lightweight clothing and no shoes during weighing. The vital signs performed on Day 1 of the Treatment Period will serve as the baseline for clinical assessment.

12-Lead Electrocardiogram

A 12-lead resting ECG will be obtained at the visits indicated in [Appendix C](#). The ECG should be performed prior to blood collection.

The ECG will be evaluated by an appropriately trained physician at the site ("local reader"). The local reader from the site will sign, and date all ECG tracings and will provide his/her global interpretation as a written comment on the tracing using the following categories:

- Normal ECG
- Abnormal ECG – not clinically significant
- Abnormal ECG – clinically significant

Only the local reader's evaluation of the ECG will be collected and documented in the subject's source. The automatic machine reading (i.e., machine-generated measurements and interpretation that are automatically printed on the ECG tracing) will not be collected.

Clinical Laboratory Tests

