8.1.2.4 Subgroup Analysis

The subgroup analyses will be performed based on the combined treatment groups. The percentage of subjects with SVR₁₂ will be calculated, as will the corresponding two sided 95% Wilson score intervals, for the following subgroups:

- HCV genotype and available subtype
- Sex
- Age
- Race
- Baseline HCV RNA level
- Baseline fibrosis stage
- Baseline cirrhosis status
- Baseline platelet count

- Baseline albumin
- Chronic Kidney Disease Stage
- HIV co-infection
- HIV ART regimen (for HIV coinfected)
- Baseline CD4+ count (for HIV coinfected)

Further details about subgroup analysis will be described in the statistical analysis plan.

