7.1 Demographic and Baseline Characteristics

Categorical demographic and baseline characteristic variables will be summarized with the number and percentage of subjects in each category. Continuous variables will be summarized with descriptive statistics (number of non-missing observations, mean, standard deviation, median, maximum and minimum). For categorical variables, the number of missing observations will be displayed, if applicable, on the summary tables. Percentages will be calculated based on the number of non-missing observations.

Continuous demographic and baseline characteristics include age, weight, height, body mass index (BMI), baseline log₁₀ HCV RNA level, creatinine clearance (Cockcroft-Gault calculation), eGFR (using the modification of diet in renal disease [MDRD] formula), platelet count, albumin, GGT, APRI, FIB-4, AST, ALT, and total, direct and indirect bilirubin.

Categorical demographic and baseline characteristics include:

- Age (< 65 or ≥ 65 years) and (< 75 or ≥ 75 years);
- Sex (male or female);

- Race (White, Black/African-American, Asian, American Indian or Alaska Native, or Native Hawaiian or Other Pacific Islander) and black race (black or non-black);
- Ethnicity (Hispanic or Latino, Not Hispanic or Latino);
- Baseline BMI (< 30 or ≥ 30 kg/m²);
- HCV genotype and subtype (using central laboratory results and final genotype/subtype results, see Section 10.8);
- Cirrhosis status (yes/no);
- Chronic Kidney Disease stage (Stage 1, 2, 3, 4, or 5);
- Baseline HCV RNA level ($< 1,000,000$; $\geq 1,000,000$ to $< 2,000,000$; or $\geq 2,000,000$ IU/mL);
- Baseline platelet count (< 90 or $\geq 90 \times 10^9/L$);
- Baseline albumin (< 35 or ≥ 35 g/L);
- Baseline eGFR (< 15 , ≥ 15 to < 30 , ≥ 30 to < 45 , ≥ 45 to < 60 , or ≥ 60 mL/min/1.73 m²);
- Baseline creatinine clearance (< 15 , ≥ 15 to < 30 , ≥ 30 to < 45 , ≥ 45 to < 60 , or ≥ 60 mL/min);
- Baseline fibrosis stage (equivalent to Metavir F0 - F1, F2, F3, or F4);
- Concomitant use of Proton Pump Inhibitors (PPIs) (yes/no);
- Tobacco use (current, former, never, or unknown);
- Alcohol use (current, former, never, or unknown);
- Injection drug use (yes, within last 12 months; yes, more than 12 months ago; or no);
- Use of stable opiate substitution (yes/no);
- History of diabetes (yes/no);
- History of depression or bipolar disorder (yes/no);
- History of bleeding disorders (yes/no);
- History of cardiovascular disease (yes/no);

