In addition, for cirrhotic subjects, the following will be summarized:

- Baseline Child-Pugh score (5, 6, or > 6).

Summaries of baseline resistance are described in Section 10.8.

Any concomitant medication coded to the WHO Drug Dictionary ATC code of A02BC will be counted as a PPI.

Baseline CKD categorization is defined according to eGFR as shown in Table 4 below:

Table 4. Definition of Chronic Kidney Disease Stages

CKD Stage	eGFR (mL/min/1.73 m ²)*
1	≥ 90
2	60 to < 90
3	30 to < 60
4	15 to < 30
5	< 15 or requiring dialysis

* $eGFR (mL/min/1.73 m^2) = 175 \times (\text{Serum Creatinine})^{-1.154} \times \text{Age}^{-0.203} \times (0.742 \text{ if female}) \times (1.21 \text{ if black})$.

Subjects will be determined to be requiring dialysis based on the Medical History (MH) eCRF. Requiring dialysis is defined as having medical history coded with any of the Preferred Terms or Lowest Level Terms specified Table 5.

Table 5. Dialysis Related Preferred Terms and Lowest Level Terms

Category	Preferred Term	Lowest Level Term
Dialysis	Artificial kidney device user	Haemodialysis fistula thrombosis
	Dialysis	Dialysis access malfunction
	Dialysis device insertion	Dialysis induced hypertension
	Haemodialysis	Hypotension during dialysis
	Haemofiltration	Thrombosis prophylaxis in hemodialysis
	Peritoneal dialysis	Dialysis device complication
	Renal replacement therapy	Dialysis dementia
	Bloody peritoneal effluent	Dialysis efficacy test
	Dialysis amyloidosis	Dependence on renal dialysis
	Dialysis disequilibrium syndrome	Artificial kidney clotting during dialysis
	Dialysis membrane reaction	Blood leak in dialyser
	Dialysis related complication	
	Extensive interdialytic weight gain	
	Haemodialysis complication	
	Haemodialysis-induced symptom	
	Inadequate haemodialysis	
	Intradialytic parenteral nutrition	
	Peritoneal cloudy effluent	
	Peritoneal dialysis complication	
	Peritoneal effluent abnormal	
	Peritoneal effluent erythrocyte count increased	
	Peritoneal effluent leukocyte count increased	
	Ultrafiltration failure	

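### SAP 7.1 counts any dialysis term in medical history as requiring dialysis, so a subject with past, resolved dialysis is staged as CKD 5 whatever the eGFR

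*Protocol*

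**What the plan says.** The protocol admits the whole renal range: in section 5.2, "subjects at all CKD stages (CKD Stages 1 – 5) are allowed to participate". Criterion 11 in section 5.2.1 then speaks of subjects now on dialysis: "Subjects requiring dialysis should have been receiving dialysis for at least 1 month prior to enrollment, and may be on hemodialysis or peritoneal dialysis". Under Medical History in section 5.3.1.1, "A complete medical history, including history of tobacco, alcohol and drug use, will be taken from each subject at Screening Visit", with an update on Day 1. Nothing limits this to ongoing conditions.

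SAP 7.1, Table 4, stages CKD by baseline eGFR with one exception: Stage 5 is "< 15 or requiring dialysis". The source for the exception is the history form: "Subjects will be determined to be requiring dialysis based on the Medical History (MH) eCRF". The rule is "Requiring dialysis is defined as having medical history coded with any of the Preferred Terms or Lowest Level Terms specified Table 5". Table 5 mixes procedures (such as Haemofiltration, Dialysis device insertion and Renal replacement therapy) with complications of dialysis. The rule has no end date, ongoing flag, minimum duration or look-back period.

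CKD stage is a categorical baseline characteristic in SAP 7.1. Protocol 8.1.2.4 lists "Chronic Kidney Disease Stage" among the SVR12 subgroups. SAP 10.6 does not list it and uses bands of baseline eGFR and creatinine clearance instead. SAP 12.1, which records changes from the protocol, mentions only the HIV-related removals.

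**The concern.** The label describes the present and the derivation describes the whole past. A complete history will include a resolved episode, for example dialysis during acute kidney injury years earlier. Because Table 4 joins its two limbs with 'or', one such record settles the stage and the measured eGFR is not consulted.

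SAP 7.2 shows the contrast. Diabetes, bleeding disorders, depression or bipolar disorder and cardiovascular disease are also derived from undated history terms, but they are reported as histories, which is what the method delivers. For dialysis the same method feeds a current-state class.

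What is at stake is descriptive. Protocol 5.6.1 and 5.6.3 name severe renal disease as a subpopulation the study is designed to include. A reader will look to the CKD-stage row to see how many such patients were studied, and that row could include subjects who are not in that state.

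**Working it through.** No figure in the plan is at issue, so there is none to reproduce. The check has two parts.

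**Can such a subject reach the rule?**
1. Eligibility: all CKD stages may enrol. Criterion 11 constrains only those who require dialysis, so someone who no longer does is not barred by it.
2. Capture: the history is complete, so a past episode can be recorded and coded to a Table 5 term.
3. Derivation: a matching term is sufficient under SAP 7.1.
4. Staging: the second limb of Table 4 gives Stage 5 at any eGFR.

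**What does the rule do to the stage?** Inputs from SAP 7.1 are the MDRD formula and the Table 4 cut-offs. Assumptions (mine, for illustration) are a male, non-black subject aged 50, so that the sex and race factors are 1, and four serum creatinine values in mg/dL.

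eGFR = 175 × SCr^(−1.154) × Age^(−0.203)

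At age 50, 175 × 50^(−0.203) = 79.09. Multiplying by SCr^(−1.154):

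| SCr | SCr^(−1.154) | eGFR | Stage by eGFR | Stage with any Table 5 term |
|---|---|---|---|---|
| 0.8 | 1.2937 | 102.3 | 1 | 5 |
| 1.0 | 1.0000 | 79.1 | 2 | 5 |
| 1.3 | 0.7388 | 58.4 | 3 | 5 |
| 2.0 | 0.4494 | 35.5 | 3 | 5 |

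**Where does the class go?**
- Baseline summary of CKD stage (SAP 7.1): affected.
- CKD-stage SVR12 subgroup (Protocol 8.1.2.4): affected if run.
- eGFR and creatinine-clearance subgroups (SAP 10.6): not affected, because neither uses the dialysis flag.
- Primary and secondary efficacy and safety: not affected, because they are analysed on the overall population.
- Enrolment monitoring: not affected, because its targets concern genotype and fibrosis stage only.

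**How many subjects?** If m subjects are wrongly placed and n are truly Stage 5, the Stage 5 count is overstated by m/n. The documents give neither number. On pure assumption, m from 0 to 2 and n from 3 to 10 gives 0 to 2/3 = 67%. That range shows only that a small group is sensitive to one or two subjects. It does not estimate the error.

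**The case against.** The strongest reply is that little hangs on this. The SAP's own renal subgroups use bands that ignore the flag, so a subject with eGFR 79.1 sits in the 60 to below 90 band. What remains is one descriptive row, in a table that also reports eGFR and creatinine clearance. Nothing indicates that a subject with past-only dialysis was enrolled. One route to recovered function is also closed: Exclusion 8 bars organ transplant recipients unless the organ has been removed or no longer functions. All of this stands, and it keeps the point minor.

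The neighbouring eGFR rows do not fully repair the matter. A Stage 5 count above the count with eGFR below 15 would show that the dialysis limb had acted, but not whether it had acted correctly. A current dialysis patient with a higher eGFR produces the same excess.

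A second reply is that Table 5 is deliberately broad so as not to miss dialysis patients, and that simply requiring an ongoing term would lose some. This is sound. Terms such as Haemodialysis fistula thrombosis or Hypotension during dialysis are point events and may carry an end date in someone still on dialysis. The fix has to allow for it.

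A reader might also infer that the SAP contradicts the protocol's eligibility rule. The documents do not support that. Criterion 11 sets how long dialysis must have been received before enrolment and does not define CKD stage. It matters here only because it uses the same expression for a present state.

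**Conclusion.** The point holds as a defect in a stated derivation. SAP 7.1 defines a current state by an undated history term, and Table 4 lets that term override eGFR. Read literally, a subject with past, resolved dialysis is staged as CKD 5. The reach is the CKD-stage baseline row, plus the protocol's CKD-stage subgroup if it is produced. The size is unknown and may be zero.

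Two stronger conclusions are tempting and should not be drawn. One is that the renal SVR12 results are distorted: the SAP's listed renal subgroups do not use the flag, so this would arise only if the CKD-stage subgroup were run. The other is that the derivation can only overstate Stage 5. A past-only term does move a subject upward. But a current dialysis patient whose history is coded outside Table 5, with eGFR of 15 or more, would be missed, so the derivation as a whole can err either way.

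The verdict assumes that the SAP is programmed as written and that the history form can hold resolved episodes, as a complete history implies.

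**What to change.** In SAP 7.1, use Table 5 terms to identify subjects for review, not to settle the class. Assign requiring dialysis only where the medical-history records show that dialysis was current at Day 1: either an ongoing dialysis record, or a dialysis-complication term in a subject confirmed to be on dialysis. Stage all others by baseline eGFR, and list subjects whose terms are past only. No eligibility or treatment rule changes.

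The cost is a sentence or two in the SAP, a small change to the derivation and a brief case review of the flagged subjects, who should be few. The documents do not show whether the history form has an ongoing or end-date field. If it has none, the case review carries the whole decision and should be completed and documented before database lock.
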